Individuals who underweight small probabilities are less likely to invest in preventive care and to adopt healthier behaviour in response to CVD risks of 10% or so that are significant in terms of potential health impact but are considered small in characterizations of the distribution of probability weights. These individuals are thus likely to be in greater need for preventive interventions and may benefit most from the medication and counselling delivered by PhilPEN.

Test:

• We will run the instrumental variable regression $Y_{it} = \gamma Y_{it-1} + \beta x_{it-1} + \tau \hat{s_i} + \mu_{it}$ as described in [H6a] separately for individuals with $\alpha_i > 1$ and individuals with $\alpha_i \le 1$. A significantly larger $\hat{\tau}$ for individuals with $\alpha_i > 1$ supports the hypothesis.

4. Elicitation of risk perceptions

Elicitation of subjective probabilities of future cardiovascular events is a key input to our analysis of the role of CVD risk perceptions in determining health behaviour and demand for primary prevention. Although the collection of expectations data is complicated by the limited formal education and numeracy skills of most of our sample, there is accumulating evidence that, if questionnaires are carefully designed, the measurement of such beliefs in the developing world is both feasible and valuable (Attanasio, 2009; Delavande et al., 2011a).

Asking respondents directly for probabilities or percent chances is often considered too abstract for developing country settings. Visual aids are commonly used (Attanasio, 2009). For example, the respondent can be asked to allocate physical objects, like beans or stones, representing probability units into a number of bins (Delavande et al., 2011b). Hill (2009) asks coffee farmers in Uganda to distribute 20 beans across three piles representing different price categories in accordance with their predictions of

future coffee prices. Attanasio et al. (2005) ask respondents to indicate a point on a ruler graded from 0 to 100 that corresponds to the likelihood of receiving income in excess of a certain amount.

To mitigate concerns that our respondents might be unfamiliar with the formal concept of probability, we will ask them to mark a number of coloured dots from 100 arranged in a square on a tablet screen (Figure 1). The respondent is asked a question, such as: "What do you think is the chance that you will have a heart attack or a stroke within the next 10 years?" The interviewer shows the respondent the square of dots and instructs her to mark the number that she thinks corresponds to that chance. When marked, the dots change colour. The respondent's reported probability, i.e. the number of marked dots, is also visible to the respondent as a number next to the figure. A similar approach has been used by Kerwin (2016), who uses a diagram of 100 pairs of stick figures representing couples, to elicit perceptions of the HIV transmission rate.

35

Figure 1 Belief elicitation tool

A potential concern when asking expectations questions is the tendency for probabilities to heap at the "focal" probability of 50%. This response may reflect the respondent's uncertainty about the probability rather than a precise evaluation that there is a 50:50 chance of the event occurring (Delavande and Kohler, 2009). In training questions, we follow the Health and Retirement Study and Kerwin (2016) by asking respondents who report 50% whether they really believe that the probability is 50%, or whether they are just not sure. This forces the respondent to consider what a response of 50% really means, and it gives us the option to control for respondents who have a tendency to give a focal response when they are not sure.

The risk perceptions module consists of eight sections. The first section familiarizes the respondent with probabilities and use of the belief elicitation tool. It starts with a simple explanation of probabilities using the example of the chance of a destructive earthquake within the following 12 months. The respondent then has to answer a number of expectations questions related to the example. The answers are used to test whether the elicited beliefs are consistent with basic properties of probabilities, such as monotonicity.

Section 2 asks the respondent to report the chance that someone of the same age and gender will have a heart attack or a stroke within ten years. This is interpreted as the respondent's perception of the CVD base rate. Section 3, as well as Sections 5-7, is completed only by respondents in the information treatment group. These sections are described in the next section of this document. In section 4, the respondent is asked to report the chance that she will have a heart attack or a stroke in the next ten years. This is interpreted as the prior belief of personal CVD risk. In Section 8, the respondent is asked to report what her chance of a heart attack or stroke within ten years would be if she were to adopt healthier behaviour, i.e. to quit smoking (if a smoker) and to control blood pressure and weight.

After stating her perceived CVD risk in Sections 2 and 4 (and 6), the respondent is asked how confident she is in her answer on a five-point scale ranging from 1 (not at all confident) to 5 (extremely confident).

Respondents are likely to differ in how certain they are that the stated probability is close to the actual probability of having a heart attack or a stroke. Moreover, in Section 4 (and 6) the participant is asked how worried she is about having a heart attack or a stroke on a five-point scale ranging from 1 (not at all worried) to 5 (extremely worried).

5. Interventions

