[H2a] Perceived CVD and diabetes risks, perceived life expectancies and subjective survival probabilities are correlated with objective risks predicted from risk factors, including demographics, BMI etc.

Test:

- Regress perceived personal risks from both information treatment group and control group on 10year CVD risk predicted from Globorisk, 10-year diabetes risk predicted from Finnish Diabetes Risk Score (FINDRISC) (Lindstrom and Tuomilehto 2003) and lifetable survival probabilities.³
- Data from section D prior to treatment group receiving information on personal CVD risk.

[H2b] Perceived CVD and diabetes risks, and perceived life expectancies, deviate from predicted risks due to differential weighting of risk factors.

Test:

- Regress perceived personal risks of both information treatment group and control group (section D) on risk factors and compare coefficients with those obtained from regression of predicted probabilities on risk factors. For example, for personal 10-year CVD risk, compare coefficients from model of reported probability to those used in Globorisk risk prediction tool to produce predicted probabilities. Moreover, compare other coefficients to those found in previous literature on the determinants of CVD and diabetes risks, and on life expectancies, such as, family history and exercise.
- Regress perceived personal CVD and diabetes risks, life expectancies and subjective survival probabilities (section D) on the respective perceived base rates (section B) and on risk factors to test the extent to which perceived personal risks are based on perceived base rates with an adjustment to make use of information available to the respondent on risk factors.

[H2c] Perceived base rates for CVD, diabetes, life expectancy and survival probability are higher than objective (predicted) base rates.

Tests:

- Compute mean deviations of perceived base rates (section B) from predicted base rates. A positive (negative) mean deviation hints at overestimation (underestimation) of CVD prevalence/diabetes prevalence/life expectancy/survival probability.
- Compute mean ratios of perceived base rates to objective (predicted) base rates. A mean ratio > 1 (< 1) hints at overestimation (underestimation) of CVD prevalence/diabetes prevalence/life expectancy/survival probability.
- Compare proportion of sample with perceived base rate < objective (predicted) base rate with proportion with perceived base rate > objective base rate.

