³ This test could be conducted using all survey respondents, including those in the lottery intervention arm. The reason we exclude the latter is because later tests make use of the information intervention and we want to have a consistent sample throughout.

[H2d] The accuracy of base rate estimates varies with education, personal risks, life expectancies and survival probabilities, the respondent's confidence in the accuracy of his perceived base rate, the respondent's degree of worry about CVDs, the respondent's degree of dispositional optimism, and possibly other characteristics.

Tests:

- Repeat computation of mean deviations and mean ratios as explained in [H2c] for each gender/age category combination and check whether CVD/diabetes prevalence, life expectancy and survival probabilities are systematically (by factors defined in [H2d]) over- or underestimated.
- Regress mean square estimation error ((perceived predicted)²) and binary indicator of whether base rate has been over- or underestimated on education level, predicted personal CVD/diabetes risk, predicted life expectancies and survival probabilities, confidence about own base rate estimates, worry about CVDs, dispositional optimism, and possibly other characteristics.

[H2e] Perceived personal CVD risk is negatively correlated with perceived life expectancies and survival probabilities.

- Regress perceived personal CVD risk on perceived life expectancies and on survival probabilities until the age of 80 years (section D).
- Compute fraction of respondents who state a perceived life expectancy conditional on experiencing a CVD event lower than their unconditional perceived life expectancy.

[H2f] Perceived personal CVD and diabetes risks, life expectancies and subjective survival probabilities deviate systematically from base rates with a tendency towards optimism bias.

Tests:

- Compute mean deviations of prior perceived personal risk (section D) from predicted base rate for treatment and control group. A negative mean deviation is consistent with optimism bias.
- Compare the mean deviation of the treatment group that is given information on the base rate (section C) with the control group that is not. Establish the extent to which under-/over-estimation of the base rate contributes to apparent optimism/pessimism bias.
- Compute mean ratio of perceived personal risk to predicted base rate for treatment and control group. A mean ratio < 1 is consistent with optimism bias.

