D _T , D _C	Effect of base rate CVD risk information on perceived personal CVD risk.

F_T, D_C	Effect of information base rate + personal CVD risk information on
	perceived personal CVD risk.
H _T , H _C	Effect of base rate + personal + reduced risk factor CVD risk information
	on perceived personal CVD risk if reduced risk factors.
F_T - H_T , D_C - H_C	Effect of information on change in CVD risk if reduced risk factors on
	perception of that change.

- Using the treatment group only, we obtain an alternative estimate of the effect of being informed of predicted personal CVD risk on perceived personal CVD risk by regressing the latter on an indicator of whether it is measured prior to or after receiving personal risk information. That is, a simple before-after comparison: $p_i = x_i \beta + \gamma 1 (p_i = F_{Ti}) + u_i$, $p_i = D_{Ti}$ or F_{Ti} .
- We will run similar regressions to test for updating of confidence about reported risks and worry about CVD risk. See the last point under [H5a] on the relevance of the impact of information on belief confidence.

[H3b] Individuals who are exposed to the information intervention do not simply memorize numbers and percentages they are told in the treatment, but incorporate the information to update beliefs about event likelihoods related to CVD risks.

Test:

• Estimate the correlation between the prior-posterior change in perceived life expectancy and the prior-posterior change in perceived 10-year CVD risk. A negative correlation means that individuals update their life expectancy in a direction consistent with their revision to perceived personal CVD risk. For example, if the perception of CVD risk is raised, then life expectancy is reduced. We will repeat the same exercise for life expectancies conditional on experiencing a heart attack/stroke. As survival probabilities conditional on a CVD event are independent of CVD risk, a coefficient of zero is consistent with Bayesian updating. We use the same beliefs as described in [H3b] to test for updating following the provision of both base rate and personal CVD risks and the provision of only personal CVD risks.

[H3c] Updating of beliefs is heterogeneous with respect to education, predicted CVD risk, confidence about CVD risk estimates and worry about CVD events.

Test:

• Repeat regression (3.1) allowing λ to vary with the stated characteristics.

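### For perceived CVD risk, H2a and H2b's first regression pool uninformed control beliefs with information-arm beliefs recorded just after that arm is told its Globorisk age-sex risk

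*Combined protocol and SAP*

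**What the plan says.** All places are in the combined protocol and SAP.

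- **Section 3.2, H2a.** The test is to "Regress perceived personal risks from both information treatment group and control group on" the Globorisk prediction (with other scores for diabetes and survival). The stated safeguard is "Data from section D prior to treatment group receiving information on personal CVD risk".
- **Section 3.2, H2b, first regression.** "Regress perceived personal risks of both information treatment group and control group (section D) on risk factors", with the coefficients then compared with Globorisk's. The hypothesis is that perceived risks "deviate from predicted risks due to differential weighting of risk factors".
- **Section 3.2, Table 1.** Section C, information on average CVD risk, comes before section D and is given to the treatment group only. Section 4 confirms this: "Section 3, as well as Sections 5-7, is completed only by respondents in the information treatment group".
- **Section 5.2.** The section C figure is a Globorisk prediction that uses only age and sex. It is given directly before the respondent states a personal risk.
- **Section 3.2, H2f.** One test compares "the treatment group that is given information on the base rate (section C) with the control group that is not".
- **Section 3.2, H3a table.** The contrast of D_T with D_C is labelled "Effect of base rate CVD risk information on perceived personal CVD risk".
- **Section 3.2, footnote 3.** The lottery arm is left out of H2a because "we want to have a consistent sample throughout".

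Neither H2a nor H2b's first regression states an arm term, an interaction or a control-only fit.

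**The concern.** H2a and H2b are meant to describe beliefs as respondents hold them: whether those beliefs track objective risk, and how people weight their own risk factors. In the information arm the section D answer is not an untouched belief, because a Globorisk number has just been supplied. Regressing that answer on Globorisk, or comparing its coefficients with Globorisk's, is partly circular.

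The safeguard in H2a covers information on personal risk only, so it does not reach section C. H2f and H3a treat D_T and D_C as differing by exactly this information, yet H2a and H2b's first regression pool them. What is at stake is interpretation: part of a pattern reported as respondents' own weighting could be a response to the intervention.

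**Working it through.** **1. Informed share.** The plan's arm sizes reproduce. For mean CVD risk, with effect 0.2 × 0.6 = 0.12 SD, two-sided 5% and 80% power, the unadjusted size is 1,091 per arm. Multiplying by (1 + 9 × 0.1) × (1 − 0.6²) = 1.216 gives 1,327, against 1,306 in Table 6. The information arm follows from 1/n = 0.2²/K − 1/1,306, with K = (1.960 + 0.842)² × 1.216. This gives 292, against 287.

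The sample is set by the binary column: f = 299/(299 + 1,361) = 299/1,660 = 0.180. The mean-risk column gives 287/1,593 = 0.180. These are follow-up targets (299 + 1,361 + 1,361 = 3,021, Table 6's follow-up total). Section D is asked at baseline, where counts are larger; the share is assumed to be the same there.

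**2. Two updating rules.** Neither is fixed by the documents. Let w be the weight put on the told figure, s the control-arm slope of belief on Globorisk risk, b the slope of the told age-sex risk on Globorisk risk, and p the slope of the respondent's own perceived base rate on Globorisk risk. Randomization supports an equal spread of predictors in the arms, so the pooled slope is (1 − f) × control slope + f × informed slope.

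- *Averaging:* informed belief = (1 − w) × own belief + w × told figure. H2a slope shift = f·w·(b − s).
- *Base-rate replacement:* the told figure displaces only the perceived base rate, and a risk-factor adjustment is added as before. This follows the structure that H2b's second regression describes. H2a slope shift = f·w·(b − p).

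**3. H2a under averaging** (b from 0.5 to 0.9; w, b and s all assumed):

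| s | w = 0.1 | w = 0.5 |
|---|---|---|
| 0 | +0.009 to +0.016 | +0.045 to +0.081 |
| 0.30 | +0.004 to +0.011 | +0.018 to +0.054 |
| 1.0 | −0.009 to −0.002 | −0.045 to −0.009 |

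The shift is zero if w = 0 or s = b. Under replacement, p takes the place of s and the zero condition becomes w = 0 or p = b.

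**4. Against sampling error.** SE = SD(belief)/(SD(predicted) × √1,660), ignoring clustering. With predicted-risk SD 11.35/5 = 2.27 (section 10.1) and an assumed belief SD of 10 to 25, SE = 0.11 to 0.27. The s = 0 shift is then 0.03 to 0.15 SE at w = 0.1 and 0.17 to 0.75 SE at w = 0.5. With an assumed predicted-risk SD of 6 it is 0.09 to 0.40 SE and 0.44 to 1.98 SE. Baseline counts are larger: allowing for 10% attrition alone, 1,660/0.9 = 1,844, so SEs are about 5% smaller.

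**5. H2b.**

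- *Smoking, BMI, blood pressure:* under averaging these coefficients are multiplied by 1 − f·w, which is 0.982 at w = 0.1 and 0.910 at w = 0.5. Under replacement they do not change, provided the perceived base rate does not itself vary with them given age and sex.
- *Age and sex:* under averaging the shift is f·w × (told coefficient − own coefficient). Replacement gives the same shift if the adjustment does not involve age or sex.

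Suppose the true weight is a uniform 0.30 of Globorisk's coefficients. Let k be the age-sex-only coefficient divided by Globorisk's conditional one (assumed 0.8, 1 or 1.3). The pooled age-sex weight is 0.30 + f·w·(k − 0.30):

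| w | age-sex, k = 0.8 / 1 / 1.3 | other factors, averaging | other factors, replacement |
|---|---|---|---|
| 0.1 | 0.309 / 0.313 / 0.318 | 0.295 | 0.300 |
| 0.5 | 0.345 / 0.363 / 0.390 | 0.273 | 0.300 |

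**6. An arm dummy alone.** It absorbs a mean shift but leaves the slope a blend of the two arms. In a simulation under averaging with illustrative coefficients (s = 0.30, w = 0.5, b = 0.817), the pooled slope was 0.346 (formula 0.347). It stayed at 0.346 with a dummy. The control-arm slope in the fully interacted model was 0.300.

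**The case against.** The strongest reply is that no material bias is shown. None of w, b, s, p or k is in the documents. With the one predicted-risk SD that they imply (2.27), the H2a shift stays below one standard error over the range tried. H2a asks only whether beliefs correlate with predicted risk, and at s = 0.30 or 1.0 a shift of at most 0.054 would not change the sign. This stands as a limit on size. It does not make the pooled slope a description of uninformed beliefs, and the plan cannot know in advance that the response to section C will be small.

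A reader might infer that pooling necessarily shrinks the smoking, BMI and blood-pressure coefficients and so creates the pattern H2b looks for. The documents do not support that. The shrinkage follows only under averaging; under base-rate replacement those coefficients are untouched.

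The plan also makes the issue partly visible. H3a estimates the mean difference between D_T and D_C, and H2f reports by arm and has a control-only test. That shows whether section C moved average beliefs, but not whether it changed slopes. Footnote 3 gives a deliberate reason for the sample; an interacted model respects it. Calling D_T a prior is right for the H3a updating test, where it precedes the personal information, but it does not make D_T an uninformed belief.

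**Conclusion.** The point holds as a matter of design. For perceived CVD risk, H2a and H2b's first regression combine about 82% uninformed and 18% informed answers without separating their slopes. If the told figure moves beliefs, the age and sex coefficients in H2b shift toward those of the told prediction. The other H2b coefficients shrink or stay put according to the updating rule. The H2a slope can rise, fall or stay the same, so a general claim that pooling inflates H2a would go too far. There is no bias if w = 0.

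The size is unknown and may be negligible; every figure above other than the 18% share and the 2.27 SD rests on assumed values. The point is confined to CVD beliefs, since section C as described gives only CVD information. These are baseline belief analyses. A reader might infer damage to the treatment comparisons on the principal outcome; nothing here touches them. A correction to the analysis text is warranted.

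**What to change.** For the CVD-belief regressions in H2a and H2b's first regression:

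- Keep the information and control sample that footnote 3 asks for.
- Include an information-arm indicator and its interaction with every predictor.
- Report the control-arm slopes as primary, and use these in the comparison with Globorisk's coefficients.
- Report the pooled fit as a sensitivity analysis.

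Footnote 3 needs no change. A control-only fit gives the same primary slopes. Control plus lottery (2,722 at Table 6's follow-up targets) would recover precision, but it departs from footnote 3, and the consent form in lottery barangays carries an extra line (section 5.3).

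The cost is text only, with no new data. The primary slopes rest on 18% fewer respondents than the pooled fit, so standard errors are larger by a factor of √(1,660/1,361) = 1.104, about 10%. The ratio is the same at baseline if the arm shares are.

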By using the Globorisk risk prediction model (Ueda et al, 2017), we avoid the limitations of the WHO/ISH charts. The Globorisk study used data on individuals with no history of CVD from eight US cohort studies to estimate models for the probability of experiencing fatal or non-fatal heart attack or stroke over a period of 10 years (Hajifathalian et al, 2015; Ueda et al, 2017). The models were then recalibrated using country-specific data on CVD incidence rates (derived from mortality rates) and on risk factor prevalence rates to obtain risk charts for 182 countries. These are the first country-specific CVD risk charts to have been derived using a consistent methodology. The models perform well in validation analysis using data from non-US health surveys. The office-based Globorisk risk algorithm, which substitutes BMI for data on diabetes and cholesterol, has been shown to predict the same risk classification as the laboratory-based version in 80% of cases, although it substantially underestimates risk for individuals with diabetes (Ueda, et al, 2017).

Globorisk allows us to predict CVD risks specific to the Filipino population, while the WHO/ISH charts are calibrated only for the population of the Western Pacific Region. Given we are not able to measure blood glucose and lipids, the office-based Globorisk is particularly valuable. The WHO/ISH chart that does not use information in cholesterol achieves this by simply entering the same (average) cholesterol value for all individuals. Entering reported diagnosed diabetes in the WHO/ISH charts will result in gross underestimation of risk for all with undiagnosed diabetes. We will avoid this by excluding individuals from the information intervention who report a diagnosis of diabetes and using the office-based Globorisk.

One disadvantage of using the Globorisk algorithm is that the information treatment group respondents will be given a risk prediction that may be inconsistent with what they are told in PhilPEN screening using the WHO/ISH chart at a RHU/CHC. However, this would happen anyway even if we were to use the WHO/ISH charts since the prediction done at the facility would use more information (on blood glucose, a different measure of blood pressure and, possibly, cholesterol). In any case, we will emphasize to each respondent that we are not informing of their own personal risk, but rather the predicted risk for a person with a similar risk factor profile to them.

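### H2b cannot tell mis-weighting of particular risk factors from a common scaling of all reported risks, and its Globorisk example may compare coefficients on different scales

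*Combined protocol and SAP*

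**What the plan says.** H2b, in section 3.2, holds that perceived risks "deviate from predicted risks due to differential weighting of risk factors". Three parts of its test matter here.

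- **Main comparison.** Regress perceived personal risk (section D of the risk perceptions module, information and control groups) on risk factors, and "compare coefficients with those obtained from regression of predicted probabilities on risk factors".
- **Worked example for CVD.** Take the coefficients of the reported-risk model and "compare coefficients from model of reported probability to those used in Globorisk risk prediction tool to produce predicted probabilities". Factors such as family history and exercise are to be compared with published coefficients.
- **Second regression.** Add the perceived base rate as a covariate, to "test the extent to which perceived personal risks are based on perceived base rates with an adjustment".

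No link function, test statistic or decision rule is given for H2b. Section 4 defines the outcome: "The respondent's reported probability, i.e. the number of marked dots", out of 100. On Globorisk, section 5.2 says that US cohort data were used to "estimate models for the probability of experiencing fatal or non-fatal heart attack or stroke over a period of 10 years", and then: "The models were then recalibrated using country-specific data on CVD incidence rates". It does not give the scale of the coefficients.

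**The concern.** Differential weighting is to be read from differences between coefficients, with no allowance for a factor common to all of them. Someone who is half as responsive to every risk factor as Globorisk, but ranks and spaces the factors identically, gives coefficients that are all half the size.

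The plan gives two reasons to expect distortion of this kind. H2c anticipates that perceived base rates are too high and measures the excess partly as a mean ratio. Section 4 warns of heaping at 50% among unsure respondents, and describes the follow-up question about 50% answers only for the training questions.

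The Globorisk example adds a possible scale mismatch. Where the plan writes out a regression of perceived risk on covariates (H3a), it is linear, so its coefficients are percentage points of risk. Coefficients inside a model that is recalibrated by country need not be.

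At stake is the reading of the belief results. Section 3.1 wants to locate the stage at which the theory of change fails. Misjudging particular factors and under-reacting to risk in general are different failures.

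**Working it through.** **Inputs from the documents.** H2b states no figure to reproduce. The linked figure is the sample size, which can be reproduced for mean CVD risk. From section 10.1 and Tables 4 and 5: SD = 11.35/5 = 2.27; difference 11.35 - 10.89 = 0.46; correlation 0.6; ICC 0.1; cluster size 10; compliance 0.6.

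- 2 x (2.8016 x 2.27/0.46)^2 x (1 - 0.36) x (1 + 9 x 0.1) = 464.8, so 47 clusters, or 470.
- 470/0.36 = 1,306 for lottery and for control.
- Information arm: 1/(2/470 - 1/1,306) = 287.

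All match Table 6. H2b then has 287 + 1,306 = 1,593 respondents, or 299 + 1,361 = 1,660 in the binary column, which is 1,660/0.9 = 1,844 at baseline before 10% attrition.

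**Algebra.** Let P be predicted risk, R reported risk, and R = a + kP + error, with the error unrelated to the factors. Regressing P on the factors gives slopes b; regressing R on the same factors gives kb. The constant a drops out, and every slope is multiplied by k. Heaping is a special case: if a share q answers 50 whatever their risk, the mean report is 50q + (1 - q)P, so k = 1 - q. With q = 0.3, a = 15 and k = 0.7. Adding the perceived base rate as a covariate does not remove a multiplier on the smoking, blood pressure and BMI slopes (reasoned, not simulated).

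**Simulation 1.** Assumptions: proportional hazards with log hazard ratios of 0.65 (age per 10 years), 0.40 (male), 0.55 (smoking), 0.18 (SBP per 10 mmHg) and 0.12 (BMI per 5 units); mean risk 11.35%, giving a predicted-risk SD of 7.8 points; mean-zero reporting noise with SD 10 or 20 points; n = 1,593 and 1,844; clustering ignored; joint robust Wald tests at 5%. Rejection rates:

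| Reports relative to Globorisk | Same-scale equality | Against internal log hazard ratios | Proportionality |
|---|---|---|---|
| Equal | 5-8% | 100% | 4-7% |
| Plus 10 points | 6-7% | 100% | 4-8% |
| Times 1.25 | 83-100% | 100% | 3-6% |
| Times 1.5 or 2 | 100% | 100% | 1-4% |
| Times 0.5 | 100% | 100% | 4-6% |
| Baseline hazard times 1.5 or 2 | 99-100% | 100% | 3-6% |

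The linear slopes of predicted risk were 6.48, 4.10, 6.55, 1.87 and 1.25 points. Age relative to smoking is 6.48/6.55 = 0.99 on this scale and 0.65/0.55 = 1.18 on the log-hazard scale, so rescaling alone does not repair the internal comparison. Fitting the reports with a complementary log-log link does: rejection falls to 4-7% for exact reporters and for inflated baseline hazards, but is 18-53% for reports multiplied by 1.5.

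**Heaping, same assumptions.** The same-scale test rejects in 3-6% of runs at q = 0, 14-31% at 0.1, 45-83% at 0.2 and 85-99% at 0.3. Proportionality rejects in 3-7% throughout.

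**Simulation 2, including the plan's smaller spread (n = 1,660).** With k = 0.5 to 0.7, the same-scale test rejects in 15-97% of runs at an SD of about 2.3 points and 59-100% at larger SDs; proportionality rejects in 3-7%. For exact reporters, same-scale rejects in 4-6% and the internal comparison in 93-100%.

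An approximate noncentrality of n(1 - k)^2 SD^2 / noise^2 explains the width of the first range:

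| k | Noise SD | Noncentrality | Power, 5 df |
|---|---|---|---|
| 0.5 | 10 | 1,660 x 0.25 x 5.15/100 = 21.4 | 97% |
| 0.5 | 20 | 5.3 | 39% |
| 0.7 | 10 | 1,660 x 0.09 x 5.15/100 = 7.7 | 55% |
| 0.7 | 20 | 1.9 | 15% |

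**The case against.** The case for leaving H2b alone has real force.

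- **The lead comparison is sound for accurate reporters.** A reader might infer that H2b flags mis-weighting in people who report exactly what Globorisk predicts. The documents do not support that: the Globorisk coefficients enter as an example, after a same-scale comparison that rejects at about the nominal rate for such people.
- **H2b does not test equality of levels.** It compares slopes, and a uniform shift of 10 points leaves the result unchanged. Level comparisons sit in H2c and H2f.
- **The scale mismatch is conditional.** Neither the link of the reported-risk model nor the scale of Globorisk's coefficients is stated, and recalibration does not establish a log-hazard scale. With a matching link, the internal comparison is legitimate.
- **No formal test is stated.** The rejection rates belong to tests supplied here. This also means that nothing in H2b separates weighting from scale.
- **Uniform under-weighting is arguably differential weighting.** The plan does not define the term. Even so, the two patterns have different explanations, and H2b as written cannot show which is present.
- **Overall responsiveness is already visible.** The slope in H2a, perceived on predicted risk, estimates k under the model above, and H2c reports mean ratios. These lower the risk of misreading but do not test whether one factor explains all the coefficients.

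Nor should one infer that a misreading would put the analysis at odds with the intervention. Sections 5.2 and 7 show that it gives the overall risk and also explains which factors raise it.

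**Conclusion.** The point holds as a gap in interpretation. H2b's same-scale comparison needs a free common factor before a coefficient difference can be credited to particular risk factors. Without one, a joint equality test rejects in 83-100% of simulated runs for common multipliers from 0.5 to 2 at a predicted-risk SD of 7.8 points, and in 15-97% for compression to 0.5 or 0.7 at the plan's SD of about 2.3. With one, rejection is 1-8% throughout.

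The Globorisk example is a mismatch only if the reported-risk model is linear and the tool's coefficients are log-hazard or similar. The first is the natural reading of the plan's other belief regressions; the second is an assumption.

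The percentages depend on assumed hazard ratios, noise and multipliers, on unbounded mean-zero noise and, in the first simulation and the heaping runs, on ignoring clustering. The scaling result is algebra and does not depend on the hazard ratios or the noise SD. H2b analyses beliefs; the principal outcome and the sample size are untouched.

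**What to change.** 1. Make the same-scale comparison the H2b analysis for CVD: regress reported and Globorisk-predicted risk on the same factors, in the same linear form, in the same respondents.
2. Estimate a common factor k and test that every reported-risk coefficient equals k times its predicted-risk counterpart, on the number of factors minus 1 df (4 for Globorisk's five predictors). Estimate the two regressions jointly, with standard errors clustered by barangay.
3. Report k as overall responsiveness next to the H2a slope. Attribute deviation to particular factors only if proportionality is rejected.
4. Drop the comparison with Globorisk's internal coefficients, or make it only with a link that matches the Globorisk model, and state that link.
5. Keep the literature comparison for family history and exercise, which are not Globorisk predictors and have no other benchmark in H2b. Label it descriptive (sign and relative size) and state its scale.

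The cost is a change of wording and one extra post-estimation test on data already planned. Non-rejection of proportionality may reflect limited power, so report the coefficient ratios with confidence intervals.
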